#### 9.5 Efficacy Analyses

#### 9.5.1 Analyses of Primary Efficacy Endpoint

The primary efficacy endpoint, proportion of subjects who achieve the modified MDA (MDA-Joints) at Week 16, will be compared between the Apremilast 30 mg BID group and placebo group using the Cochran-Mantel-Haenszel (CMH) test, controlling for use of glucocorticosteroids at baseline (yes/no) and use of a csDMARD (naïve, prior use only, or prior and concomitant use). Unadjusted group responder rates, unadjusted treatment differences in proportions, and adjusted treatment differences in proportions using the weighted average of the treatment differences across the strata with the CMH weights, along with the associated 2-sided 95% CIs using a normal approximation to the weighted average and the 2-sided p-values from the CMH tests, will be provided. Apremilast will be declared efficacious if the test result for the comparison is statistically significant in favor of Apremilast.

Subjects who have discontinued prior to Week 16 due to lack of efficacy or adverse event will be treated as non-responders in the analysis; and the multiple imputation methodology will be utilized, as appropriate, to impute the data for subjects whose

Page 49 of 67

event.

Protocol Number: 20200058 Date: 07 February 2023

modified MDA at Week 16 is missing for a reason other than lack of efficacy or adverse

The combination of non-responder imputation of some subjects and the multiple imputation of the rest of missing values at Week 16 is to address the Missing Not At Random (MNAR) nature of missing values at the analysis time point. The detailed data handling and analysis follow the procedures below:

Step 1. Censor or apply NRI (non-responder imputation) per different scenario

- (Censoring) After applying Early Termination Visit data, missing Week 16 values remain as missing for patients discontinued prior to Week 16 due to other reasons
- (NRI) Set non-responder (NR) to subjects discontinued prior to Week 16 due to
  - Lack of efficacy
  - Adverse event

Step 2. Implement multiple imputation, with 40 iterations (using fully conditional specification to impute the missing modified MDA generated from Step 1).

Step 3. Calculate statistics on each imputation iteration from Step 2.

Step 4. Combine results from Step 3.

The overall p-value will be derived from the CMH test that is normalized *via* the Wilson-Hilferty transformation (Wilson & Hilferty, 1931; Goria, 1992).

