9.6.3. Primary Efficacy Endpoint

The primary efficacy endpoint, proportion of subjects who achieve the modified MDA (MDA-Joints) at Week 16, between the Apremilast 30 mg BID and placebo groups will be compared using a Cochran-Mantel-Haenszel test, controlling for concomitant use of glucocorticosteroids at baseline (yes/no) and use of a csDMARD: (csDMARD-naïve; csDMARD use prior to baseline; or csDMARD use prior to and concomitant at baseline).

Subjects who have discontinued prior to Week 16 due to lack of efficacy or adverse event will be treated as non-responders in the analysis; and the multiple imputation methodology will be utilized to impute the data for subjects whose modified MDA at Week 16 is missing for a reason other than lack of efficacy or adverse event. Sensitivity analyses will be performed using the non-responder imputation for subjects who have discontinued prior to Week 16, or do not have sufficient information for a definitive determination of the modified MDA (MDA-Joints) status at Week 16.

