11. DISCONTINUATIONS

11.1. Treatment Discontinuation

The following events are considered sufficient reasons for discontinuing a subject from the investigational product(s):

- Adverse event(s)
- Withdrawal by subject
- Death
- Lost to follow-up
- Lack of efficacy
- Non-compliance with study drug
- Study terminated by Sponsor
- Pregnancy
- Death
- Protocol deviation
- Other (to be specified on the CRF)

The reason for discontinuation of treatment should be recorded in the CRF and in the source documents.

The decision to discontinue a subject from treatment can be taken at any time and remains the responsibility of the treating physician, which will not be delayed or refused by the Sponsor. However, prior to discontinuing a subject, the Investigator may contact the Medical Monitor and forward appropriate supporting documents for review and discussion.

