11.2. Study Discontinuation

The following events are considered sufficient reasons for discontinuing a subject from the study:

- Screen failure
- Adverse event
- Withdrawal by subject
- Death
- Loss to follow-up
- Other (to be specified on the CRF)

The reason for study discontinuation should be recorded in the CRF and in the source documents.

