# 5.2.1 Treatment-emergent Adverse Events Leading to Drug Withdrawal, Leading to Drug Interruption, and Leading to Death, and Drugrelated Treatment-emergent Adverse Events

A TEAE leading to drug withdrawal is a TEAE for which the investigator indicates that the action taken with respect to IP is withdrawn permanently (action taken on AE eCRF is recorded as "DRUG WITHDRAWN"). A TEAE leading to drug interruption is a TEAE for which the investigator indicates that the action taken with respect to IP is interrupted. A TEAE leading to death is a TEAE for which the outcome is fatal. Relationship to IP is based on the investigator's causality judgment; that is, a drug-related AE is an AE indicated by the investigator to have a suspected relationship to IP.

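### A death before Week 16 recorded under its own discontinuation reason goes to multiple imputation in the primary analysis instead of being counted as non-response

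*SAP*

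**What the plan says.** SAP 9.5.1 handles missing Week 16 MDA-Joints status in two parts. The first is non-responder imputation (NRI): "Subjects who have discontinued prior to Week 16 due to lack of efficacy or adverse event will be treated as non-responders". Step 1 repeats this as a list with two entries, lack of efficacy and adverse event. The second part covers everyone else. After any Early Termination data have been applied, "missing Week 16 values remain as missing for patients discontinued prior to Week 16 due to other reasons", and Step 2 fills those values with 40 imputations by fully conditional specification.

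Protocol 9.6.3 draws the same line. Multiple imputation is used "to impute the data for subjects whose modified MDA at Week 16 is missing for a reason other than lack of efficacy or adverse event".

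Protocol 11.1 (treatment discontinuation) lists Adverse event(s), Lack of efficacy and Death as separate entries; Death appears twice. Protocol 11.2, under "The following events are considered sufficient reasons for discontinuing a subject from the study", again lists Adverse event and Death separately. Both sections have the reason recorded in the CRF.

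For the binary secondary endpoints, SAP 9.5.2 says only that NRI and multiple imputation are used as appropriate. It gives no list of reasons. Protocol 9.6.4 says their analysis will be similar to that of the primary endpoint.

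**The concern.** Multiple imputation estimates a value that exists but was not observed. After a death there is no Week 16 joint count, pain score or HAQ-DI to recover, so drawing a response status for that subject has no sensible meaning. SAP 9.5.1 explains its mix of NRI and imputation as a way of dealing with data missing not at random; leaving death in the imputed group works against that aim.

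What is at stake is the correctness of the analysis on which efficacy is declared, which is also the first step of the testing sequence in SAP 9.1.3. The subgroup analyses (SAP 4.2) repeat the primary analysis, and the logistic regression (SAP 9.5.1) uses the same imputed data, so both inherit the gap. Two sites could also handle the same fatal case differently, one recording Death and the other Adverse event. The subject would then be imputed in one case and a fixed non-responder in the other.

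**Working it through.** No figure in the plan is in dispute here, so there is none to reproduce. The check is a trace through the text, followed by the size of the effect.

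**Trace of a subject who dies before Week 16**

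1. Recorded reason: Protocol 11.1 and 11.2 offer Death as its own entry. Assume the site chooses it.
2. Early Termination value: SAP 5.4 maps such a value to the next scheduled visit. Normally there is none after a death, so Week 16 stays empty.
3. SAP 9.5.1 Step 1: Death is neither of the two NRI entries, so the value remains missing.
4. SAP 9.5.1 Step 2: the missing status is imputed in each of 40 data sets, as responder or non-responder.
5. Search for an overriding rule: SAP 5.2.1 says "A TEAE leading to death is a TEAE for which the outcome is fatal", but this classifies the event for safety tables and is not tied to the NRI list. Elsewhere in the SAP, dates of death bound safety windows and help determine the last known date for exposure. No efficacy section assigns death to non-response.

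**Inputs for the size**

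- Total about 285 (Protocol 4.1), allocated 2:1 (SAP 3.1). Arm sizes are blacked out. Assumed: 285 × 2/3 = 190 apremilast and 285 × 1/3 = 95 placebo.
- Planning response rates of 30% and 15% (SAP 3.2), used as a rough stand-in for the probabilities the imputation model would give.
- Number of deaths in one arm before Week 16: not given; 1 to 3 assumed for illustration.

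**Average shift in the arm's response rate** = deaths × imputation probability / arm size

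- Apremilast, one death: 0.30 / 190 = 0.158 percentage points.
- Placebo, one death: 0.15 / 95 = 0.158 percentage points.
- Two deaths in one arm: 0.316 points. Three: 0.474 points.

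Under NRI the contribution would be 0 in every data set.

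**Upper limit for one death** (responder in all 40 data sets) = 1 / arm size

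- Apremilast: 1 / 190 = 0.53 points.
- Placebo: 1 / 95 = 1.05 points.

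**How often the subject is credited with response**

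- Apremilast: on average 0.30 × 40 = 12 of 40 data sets; chance of at least one is 1 − 0.70^40, above 99.99%.
- Placebo: on average 0.15 × 40 = 6 of 40; chance of at least one is 1 − 0.85^40 = 99.85%.

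**Direction:** a death on apremilast raises the estimated difference by about 0.16 points, and a death on placebo lowers it by the same amount. Against the 15-point design difference, 0.158 / 15 is about 1%.

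**The case against.** The strongest reply is that the documents treat death as the outcome of an adverse event, not as an alternative to one. Protocol 10.2.1 defines a serious adverse event as one that may result in death, Protocol 9.7 speaks of adverse events leading to death, and the sample SAE form in Appendix W asks for the cause and does not accept death as the event term. On that view, a subject with a fatal event discontinued because of an adverse event, and NRI applies. This is a reasonable account of what the authors may have meant, and it holds wherever the site records Adverse event as the reason. It does not settle the point. Those passages govern event reporting, whereas the imputation rule turns on why the subject discontinued, and the discontinuation lists keep the two reasons apart.

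The SAP also applies multiple imputation as appropriate. That leaves discretion but supplies no rule for death, while Step 1 states plainly that other reasons stay missing.

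The third reply stands in full. The prespecified NRI sensitivity analysis (SAP 9.5.1, Protocol 9.6.3) counts everyone who discontinues before Week 16 as a non-responder, so the influence of any imputed death would show there.

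Three stronger readings are tempting, and the documents do not support them. A reader might infer that the trial's result could turn on which box a site ticks; at about 0.16 points per death that is out of proportion. A reader might infer that SAP 9.5.2 states the same two-reason rule for the binary secondary endpoints; it does not, and carry-over is only a plausible inference from the protocol's description of those analyses as similar. A reader might infer an expected number of deaths from the background sections; the long-term safety text in Protocol 1.2.1.2 mentions two suicides among placebo patients in earlier studies, but the readable text gives no 16-week death rate.

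**Conclusion.** The point holds on the literal text. A subject recorded as Death before Week 16, with no mapped Early Termination value, is multiply imputed and can count as a responder in the primary analysis, unless the site records Adverse event. The size, about 0.16 percentage points of the arm rate per death, rests on three assumptions: arms of 190 and 95, planning rates in place of the unspecified imputation model, and an illustrative number of deaths. The 0.53 and 1.05 point limits depend only on the assumed arm sizes. This is a minor matter. The gain is a correct primary analysis, and correct subgroup and logistic analyses built on it; there is no material gain in power and no systematic bias towards either arm is shown.

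**What to change.** Before the Week 24 database is unblinded:

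- In SAP 9.5.1, add death before Week 16 to the non-responder sentence and to the NRI bullets in Step 1, whatever reason the site records.
- In SAP 9.5.2, state that the same list of reasons governs NRI for the binary secondary endpoints.
- In SAP Section 10, record the difference from Protocol 9.6.3, which carries the two-reason rule. That section already documents one departure made without a protocol amendment.

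The cost is a few lines of text and one extra condition in the derivation program. No new data, method or sample size is needed.

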#### Sensitivity analysis

Subjects with no response data to determine the response status at all assessment timepoints will be excluded.

The effect of protocol compliance will be studied by repeating the primary analysis using the PP population, according to the treatment subjects actually receive and the stratification factors subjects' medication data show.

In order to investigate the impact of the imputation method used for the primary analysis, a sensitivity analysis will be performed using the non-responder imputation for subjects who have discontinued prior to Week 16, or do not have sufficient information for a definitive determination of the modified MDA (MDA-Joints) status at Week 16. The responder analysis using the CMH model as in the primary analysis will be repeated.

Page 50 of 67

Protocol Number: 20200058 Date: 07 February 2023

To examine the robustness of the results obtained from the primary analysis based on the CMH method, a sensitivity analysis will be implemented using logistic regression. The responder analysis based on the logistic regression model will include treatment group, concomitant use of glucocorticosteroids at baseline (yes/no), and use of csDMARD (naïve, prior use only, or prior and concomitant use) as factors. This analysis will be based on the FAS data set used for the primary analysis with non-responder imputation along with the MI.

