6.5.5. Diarrhea, Nausea and Vomiting

Apremilast has been associated with AE reports of diarrhea in clinical trials. Most diarrhea events were of mild or moderate severity and reported within the first 2 weeks of treatment, usually resolving within 4 weeks without medical intervention.

Diarrhea is the passage of three or more loose or liquid stools per day, or more frequently than is normal for the individual (World Health Organization [WHO], 2013). Following the definition of diarrhea by the WHO and taking a more conservative approach, the AE of diarrhea in this protocol is defined as having two or more watery/liquid stools in a day.

To better characterize diarrhea and to distinguish similar events coding to the Medical Dictionary of Regulatory Activities (MedDRA) preferred term of diarrhea, subjects reporting diarrhea or similar events (eg, frequent bowel movements, loose bowels, etc.) will be asked whether they have had two or more watery/liquid stools in a day. Subjects who respond "yes" to this question will be further asked how often, on average, have they experienced two or more watery/liquid stools in a day. Subjects who respond "no" to the question will not be asked any further questions. This data will be reported via electronic data capture in the ERT tablet. If an AE is identified by the Investigator, the AE and respective attributes will be reported in the clinical database. If the AE meets serious criteria, it must be reported to Amgen Global Patient Safety (see Section 10.5).

There have been post-marketing reports of severe diarrhea, nausea, and vomiting associated with the use of apremilast. Most events occurred within the first few weeks of treatment. In some cases, patients were hospitalized.

Subjects 65 years of age or older and subjects taking medications that can lead to volume depletion or hypotension may be at a higher risk of complications. Subjects should be monitored for the occurrence of severe diarrhea, nausea and vomiting. If a subject develops severe diarrhea, nausea and vomiting, discontinuation of study treatment may be necessary (see Section 11).

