9.2. Study Population Definitions

The Full Analysis Set (FAS) will consist of all subjects who are randomized. Efficacy analyses will be primarily based on the FAS and subjects will be included in the treatment group to which they are randomized.

The Per Protocol (PP) population will consist of all subjects who receive at least one dose of study medication and have no major protocol violations during the 24-week placebo-controlled treatment period. The final determination of major protocol violations will be made prior to the unblinding of treatment assignment and will be documented. The PP analyses will be based on the PP population and subjects will be included in the treatment group for the treatment they actually receive.

The Safety population will consist of all subjects who receive at least one dose of study medication. The safety analyses will be based on the safety population and subjects will be included in the treatment group for the treatment they actually receive.

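### The SAP's sensitivity section opens with an unscoped exclusion of subjects who have no response data, which conflicts with the non-responder analysis specified in the same section

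*SAP*

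**What the plan says.** The part of SAP 9.5.1 headed Sensitivity analysis has four paragraphs.

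- The first is a single sentence: "Subjects with no response data to determine the response status at all assessment timepoints will be excluded". It names no analysis, population, model or purpose.
- The second repeats the primary analysis in the per-protocol set.
- The third is the NRI analysis. It counts as non-responders those who stopped before Week 16 and those who "do not have sufficient information for a definitive determination of the modified MDA (MDA-Joints) status at Week 16".
- The fourth is a logistic regression: "This analysis will be based on the FAS data set used for the primary analysis with non-responder imputation along with the MI".

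Protocol 9.6.3 specifies the same NRI analysis, with no exclusion: "Sensitivity analyses will be performed using the non-responder imputation for subjects who have discontinued prior to Week 16, or do not have sufficient information". On the analysis set, Protocol 9.2 says: "The Full Analysis Set (FAS) will consist of all subjects who are randomized". SAP 6.1 narrows this only by leaving out subjects who were randomised in error and never dosed.

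The primary analysis, described earlier in SAP 9.5.1, carries no exclusion. Discontinuations before Week 16 for lack of efficacy or an adverse event are non-responders, and other missing Week 16 values are multiply imputed. The readable text of SAP Section 10, on changes from the protocol, mentions no exclusion, but part of that section is blacked out.

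**The concern.** A subject with no response data at any timepoint meets both the exclusion rule and the NRI rule, and cannot be both left out and counted as a failure. As the text stands, two programmers could produce different denominators for the NRI analysis and each point to the SAP in support.

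The NRI analysis is meant to be stricter than the primary one, because it also fails the subjects whom the primary analysis multiply imputes. With the exclusion applied, a subject who stops early for an adverse event and leaves no assessments is a failure in the primary analysis but disappears from the stricter check. For that subject the check becomes more lenient than the result it is testing.

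The exclusion is also made after randomisation and could depend on tolerability. The first post-baseline visit is Week 4 (Protocol Table 13), and Protocol 6.5.5 says of apremilast: "Most diarrhea events were of mild or moderate severity and reported within the first 2 weeks of treatment". Protocol Table 8 gives diarrhea in 13.2% on 30 mg BID and 2.5% on placebo over the first 16 weeks.

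**Working it through.** **1. How each kind of subject is handled.** All three rows are subjects who stop before the Week 4 visit.

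| Subject | Primary analysis | NRI analysis as described | NRI with the exclusion applied |
|---|---|---|---|
| Adverse event or lack of efficacy, no Early Termination assessment | non-responder | non-responder | left out |
| Other reason, no Early Termination assessment | multiply imputed | non-responder | left out |
| Any reason, Early Termination visit attended | non-responder or imputed, by reason | non-responder | non-responder |

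The third row follows because the Early Termination visit includes the joint counts, VAS scales, LEI, HAQ-DI and BSA (Protocol Table 13 and 6.2.1), and SAP 5.4 maps those values to the next scheduled visit. The exclusion therefore bites only in the first two rows.

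**2. The plan's own figures.** Protocol 4.1 gives about 285 subjects. The design assumptions are 2:1 allocation, 30% versus 15%, 80% power, two-sided 0.05 and 15% dropout (SAP 3.2). With unpooled variance:

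- Placebo n = (1.960 + 0.842)² × (0.15×0.85 + 0.30×0.70/2) / 0.15² = 81.1.
- Total = 3 × 81.1 / 0.85, which rounds up to 287, or 290 if the placebo arm is first rounded up to 82.
- Power at 285 × 0.85 is 79.8%.

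So 285 is reproduced to within 3%. (The pooled-variance formula gives 279 before dropout and 329 after it.) The sample size is not in dispute; it only fixes the scale. The arm sizes are blacked out, so 190 and 95 are assumed from the 2:1 ratio.

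**3. Rate of subjects with no data.** The documents give no such rate for this trial. The nearest figure is from study PSA-006 (Protocol 1.2.1.1.3 and Table 6):

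- 110 apremilast and 109 placebo subjects were randomised.
- 109 and 109 had a baseline and at least one post-baseline HAQ-DI value. At most 1/110 = 0.9% and 0/109 = 0% therefore had none.
- HAQ-DI was observed at Week 16 in 91 and 103. Missing: 19/110 = 17.3% and 6/109 = 5.5%. These are all Week 16 gaps, not subjects without any data, so they serve only as an extreme bound.

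**4. Effect of the exclusion.** Suppose NRI on everyone gives 57/190 = 30.0% and 14.25/95 = 15.0%. If fractions a (apremilast) and b (placebo) have no data and are dropped, the responders stay and the denominators shrink:

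difference = 30.0/(1 − a) − 15.0/(1 − b).

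The last column repeats this with 15% in both arms, so that the NRI difference is zero.

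| a, b | Rates after exclusion (%) | Difference (points) | Shift from 15.0 | False difference if both arms are 15% |
|---|---|---|---|---|
| 0.9%, 0% (PSA-006) | 30.3, 15.0 | 15.3 | 0.3 | 0.1 |
| 2%, 0% | 30.6, 15.0 | 15.6 | 0.6 | 0.3 |
| 5%, 5% | 31.6, 15.8 | 15.8 | 0.8 | 0.0 |
| 5%, 2% | 31.6, 15.3 | 16.3 | 1.3 | 0.5 |
| 10%, 2% | 33.3, 15.3 | 18.0 | 3.0 | 1.4 |
| 17.3%, 5.5% (bound) | 36.3, 15.9 | 20.4 | 5.4 | 2.3 |

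All rates except those from PSA-006 are assumptions. The 10% row is already strained: it would mean that two-thirds (10/15) of the planned dropout in that arm left no assessment at all. Each arm's rate can only rise, but the difference need not. With 2% and 5% it is 30.0/0.98 − 15.0/0.95 = 30.6 − 15.8 = 14.8, slightly below 15.0.

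**The case against.** The strongest reply is that the first sentence is a separate, fourth analysis of observed data. The other three paragraphs each describe one analysis with its own data set, and a section-wide reading clashes with the explicit data set in the logistic paragraph. On that reading the fault is ambiguity rather than contradiction. The reading is possible, but the sentence lacks the purpose, method and population that the other paragraphs supply, so the SAP does not settle which is meant. The text needs correcting either way.

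A reader might also infer three stronger points, which the documents do not support:

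- **That early dropouts in general are removed.** Anyone with a Week 4 or Early Termination assessment stays in.
- **That the excluded numbers are likely to differ materially between arms.** The gastrointestinal data and the PSA-006 Week 16 missingness support the direction. However, Protocol 6.5.5 adds that the diarrhea usually resolved within 4 weeks without intervention, and the group that would actually be excluded was at most 1/110 versus 0/109 in PSA-006. The first visit there was Week 2, so the rate here could be somewhat higher.
- **That every other provision requires these subjects to be non-responders.** Only the NRI analysis makes them all failures. The definitions of the full analysis set fix membership only, and the per-protocol and logistic analyses keep multiple imputation for other reasons. The clash with the logistic analysis is therefore over its data set.

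**Conclusion.** The point holds as an unscoped rule that, read across the section, conflicts with the NRI sensitivity analysis in SAP 9.5.1 and Protocol 9.6.3 and with the data set of the logistic analysis. The size is probably small: about 0.3 points on a 15.0-point difference at the PSA-006 rate, and 0.6 to 3.0 points under wider assumed rates. These figures rest on arms of 190 and 95, NRI rates at the design values, and HAQ-DI availability in another study standing in for MDA-Joints data here.

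It would be tempting to conclude that the trial's main result is at risk. It is not: the primary analysis has no such exclusion and already fails discontinuations for adverse events, and the testing hierarchy is unaffected. The reason to act is that the conservative check has no settled denominator, and one reading of it errs in the lenient direction for each arm's rate.

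**What to change.** - Delete the opening sentence of the sensitivity part of SAP 9.5.1. If an observed-data analysis was intended, confine the sentence to one named supplementary analysis with its population stated.
- State that the NRI sensitivity analysis keeps every subject in the full analysis set, with undetermined Week 16 status counted as non-response.
- Report the number of subjects with no post-baseline response data, by arm and reason.

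The cost is one SAP edit and one small table. Compared with applying the exclusion, the NRI estimate becomes slightly less favourable. The edit should be made before the Week 24 database is unblinded, so that the denominator is not chosen afterwards. If that point has passed, the clinical study report should say which reading was used and give the NRI result on the full set.
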